9.2 Biomarkers

Fill 3 red top SST (Tiger) tubes (8.5 mL each) with blood to measure levels of sVEGFR2 and PIGF at the following time points:

- Baseline
- C2D1
- C3D1
- C4D1

Invert the tubes gently 10 times. Let the tubes stand at room temperature to coagulate for 30-60 minutes. Centrifuge within one hour of collection at 1600g for 15 minutes. Store tubes at -70°C or cooler until shipment.

SHIP FROZEN IN BATCHES TO:

[name] [name] – Research lab
[name]
[name]
[name]

9.3 Pharmacokinetics

Twenty mL of blood will be drawn at the following time points to measure plasma pazopanib concentrations:

- Baseline (prior to initiation of treatment)
- Cycle 1 Day 5 (prior to escalation to 400 mg BID)
- Cycle 1 Day 9 (prior to escalation to 800 mg QD)
- Cycle 2 Day 1

Blood should be collected in 2 EDTA purple top tubes and 1 red top tube. DNA (for future use), serum, and whole cells should be prepared and frozen down prior to shipment using standard laboratory techniques. Samples should be labeled with the corresponding patient's study ID number, initials, and date of collection.

These PKs will only be performed in the first 11 patients enrolled at Washington University. This testing was completed as of amendment 4.

SHIP FROZEN IN BATCHES TO:

[name] [name] – Research lab
[name]
[name]
[name]

10.0 STUDY CALENDAR

Screening assessments must be performed no more than 14 days prior to start of study treatment, except scans which may take place up to 28 days prior to the start of treatment. After the start of study treatment, there is a ± 7 day window for all exams, scans, labs and procedures to be performed. Please note, there is also a ± 7 day window for treatment and for routine office visits.

	Screening	D1 of each cycle	C1D5	C1D8	C1D9	C1D15 and C2D15	End of every even-numbered cycle	EOT	F/U ¹	
Informed consent	X									
PE, H&P, PS	X	X						X		
VS	X	X		X				X		
CBC	X	X		X				X		
CMP	X	X		X				X		
LFTs ²	X	X ²		X ²		X ²		X		
Pregnancy test ³	X							X		
UPC	X	X ⁴						X		
TSH, FT4	X	X ⁵								
PT/PTT, INR	X							X		
ECG	X	X ⁶								
ECHO ¹⁰	X									
CT scan	X						X	X		
Pazopanib		X	-----					X ⁷		
FACT-G		X ⁸				X ⁸				
Blood for biomarkers		X ⁹								
Collect/review drug diary		X								
Toxicity assessment	X	X						X		

1. Every 3 months until death.

2. Monitor serum liver tests (total bilirubin, ALT/AST) before initiation of treatment with pazopanib and on C1D15, C2D1, C2D15, C3D1, C4D1, C5D1, and as clinically indicated (± 3 days). Periodic monitoring should continue after C5.

3. Women of childbearing potential only.

4. D1 of each cycle through C6, then D1 of every even-numbered cycle thereafter.

5. Monitor between every 8 to every 16 weeks.

6. C2D1, C4D1, C7D1, and then every 16 weeks (D1 of every 4th cycle) until EOT.

7. To be taken PO each day. Each cycle is 4 weeks long. See Section 5.1 for dosing instructions.

8. Baseline (prior to C1D1), C1D15, and D1 of every cycle thereafter.

9. Baseline (prior to C1D1), C2D1, C3D1, and C4D1.

10. Baseline (prior to C1D1) and periodic reassessment as needed and/or as indicated. Consistent diagnostic imaging should be used throughout study.

11.0 DATA SUBMISSION SCHEDULE

Case report forms with appropriate source documentation will be completed according to the schedule listed in this section.

Case Report Form	Submission Schedule
Original Consent Form	Prior to registration
Registration Form Eligibility Form On-Study Form	Prior to starting treatment
Treatment Form Pill Diary	Every cycle
QOL Form	Baseline C1D15 Day 1 of every cycle thereafter
Correlatives Form	Baseline C1D5 C1D9 C2D1 C3D1 C4D1
Toxicity Form	Continuous
Treatment Summary Form	Completion of treatment
Follow Up Form	Every 3 months until death
Tumor Measurement Form	Baseline, end of every even numbered cycle, and end of treatment
MedWatch Form	See Section 7.0 for reporting requirements

Any queries generated by Washington University must be responded to within 28 days of receipt by the participating site. The Washington University research team will conduct a regular review of data status at all secondary sites, with appropriate corrective action to be requested as needed.

12.0 MEASUREMENT OF EFFECT

12.1 Antitumor Effect – Solid Tumors

For the purposes of this study, patients should be re-evaluated for response 8 weeks after initiation of pazopanib and then every 8 weeks thereafter. In addition to a baseline scan, confirmatory scans should also be obtained not less than 8 weeks following initial documentation of objective response.

Response and progression will be evaluated in this study using the new international criteria proposed by the revised Response Evaluation Criteria in Solid Tumors (RECIST) guideline (version 1.1) [Eur J Ca 45:228-247, 2009]. Changes in the largest

diameter (unidimensional measurement) of the tumor lesions and the shortest diameter in the case of malignant lymph nodes are used in the RECIST criteria.

12.2 Disease Parameters

Measurable disease: Measurable lesions are defined as those that can be accurately measured in at least one dimension (longest diameter to be recorded) as >20 mm by chest x-ray, as >10 mm with CT scan, or >10 mm with calipers by clinical exam. All tumor measurements must be recorded in millimeters (or decimal fractions of centimeters).

Malignant lymph nodes: To be considered pathologically enlarged and measurable, a lymph node must be >15 mm in short axis when assessed by CT scan (CT scan slice thickness recommended to be no greater than 5 mm). At baseline and in follow-up, only the short axis will be measured and followed.

Non-measurable disease: All other lesions (or sites of disease), including small lesions (longest diameter <10 mm or pathological lymph nodes with ≥ 10 to <15 mm short axis), are considered non-measurable disease. Bone lesions, leptomeningeal disease, ascites, pleural/pericardial effusions, lymphangitis cutis/pulmonitis, inflammatory breast disease, and abdominal masses (not followed by CT or MRI), are considered as non-measurable.

Note: Cystic lesions that meet the criteria for radiographically defined simple cysts should not be considered as malignant lesions (neither measurable nor non-measurable) since they are, by definition, simple cysts.

‘Cystic lesions’ thought to represent cystic metastases can be considered as measurable lesions, if they meet the definition of measurability described above. However, if non-cystic lesions are present in the same patient, these are preferred for selection as target lesions.

Target lesions: All measurable lesions up to a maximum of 2 lesions per organ and 5 lesions in total, representative of all involved organs, should be identified as target lesions and recorded and measured at baseline. Target lesions should be selected on the basis of their size (lesions with the longest diameter), be representative of all involved organs, but in addition should be those that lend themselves to reproducible repeated measurements. It may be the case that, on occasion, the largest lesion does not lend itself to reproducible measurement in which circumstance the next largest lesion which can be measured reproducibly should be selected. A sum of the diameters (longest for non-nodal lesions, short axis for nodal lesions) for all target lesions will be calculated and reported as the baseline sum diameters. If lymph nodes are to be included in the sum, then only the short axis is added into the sum. The baseline sum diameters will be used as reference to further characterize any objective tumor regression in the measurable dimension of the disease.

Non-target lesions: All other lesions (or sites of disease) including any measurable lesions over and above the 5 target lesions should be identified as non-target lesions and should also be recorded at baseline. Measurements of these lesions are not required, but the presence, absence, or in rare cases unequivocal progression of each should be noted throughout follow-up.

12.3 Methods for Evaluation of Measurable Disease

All measurements should be taken and recorded in metric notation using a ruler or calipers. All baseline evaluations should be performed as closely as possible to the beginning of treatment and never more than 4 weeks before the beginning of the treatment.

The same method of assessment and the same technique should be used to characterize each identified and reported lesion at baseline and during follow-up. Imaging-based evaluation is preferred to evaluation by clinical examination unless the lesion(s) being followed cannot be imaged but are assessable by clinical exam.

Clinical lesions: Clinical lesions will only be considered measurable when they are superficial (e.g., skin nodules and palpable lymph nodes) and ≥ 10 mm diameter as assessed using calipers (e.g., skin nodules). In the case of skin lesions, documentation by color photography, including a ruler to estimate the size of the lesion, is recommended.

Chest x-ray: Lesions on chest x-ray are acceptable as measurable lesions when they are clearly defined and surrounded by aerated lung. However, CT is preferable.

Conventional CT and MRI: This guideline has defined measurability of lesions on CT scan based on the assumption that CT slice thickness is 5 mm or less. If CT scans have slice thickness greater than 5 mm, the minimum size for a measurable lesion should be twice the slice thickness. MRI is also acceptable in certain situations (e.g. for body scans).

Use of MRI remains a complex issue. MRI has excellent contrast, spatial, and temporal resolution; however, there are many image acquisition variables involved in MRI, which greatly impact image quality, lesion conspicuity, and measurement. Furthermore, the availability of MRI is variable globally. As with CT, if an MRI is performed, the technical specifications of the scanning sequences used should be optimized for the evaluation of the type and site of disease. Furthermore, as with CT, the modality used at follow-up should be the same as was used at baseline and the lesions should be measured/assessed on the same pulse sequence. It is beyond the scope of the RECIST guidelines to prescribe specific MRI pulse sequence parameters for all scanners, body parts, and diseases. Ideally, the same type of scanner should be used and the image acquisition protocol should be followed as closely as possible to prior scans. Body scans should be performed with breath-hold scanning techniques, if possible.

PET-CT: At present, the low dose or attenuation correction CT portion of a combined PET-CT is not always of optimal diagnostic CT quality for use with RECIST measurements. However, if the site can document that the CT performed as part of a PET-CT is of identical diagnostic quality to a diagnostic CT (with IV and oral contrast), then the CT portion of the PET-CT can be used for RECIST measurements and can be used interchangeably with conventional CT in accurately measuring cancer lesions over time. Note, however, that the PET portion of the CT introduces additional data which may bias an investigator if it is not routinely or serially performed.

Ultrasound: Ultrasound is not useful in assessment of lesion size and should not be used as a method of measurement. Ultrasound examinations cannot be reproduced in their entirety for independent review at a later date and, because they are operator dependent, it cannot be guaranteed that the same technique and measurements will be taken from one assessment to the next. If new lesions are identified by ultrasound in the course of the study, confirmation by CT or MRI is advised. If there is concern about radiation exposure at CT, MRI may be used instead of CT in selected instances.

Endoscopy, Laparoscopy: The utilization of these techniques for objective tumor evaluation is not advised. However, such techniques may be useful to confirm complete pathological response when biopsies are obtained or to determine relapse in trials where recurrence following complete response (CR) or surgical resection is an endpoint.

Tumor markers: Tumor markers alone cannot be used to assess response. If markers are initially above the upper normal limit, they must normalize for a patient to be considered in complete clinical response. Specific guidelines for both CA-125 response (in recurrent ovarian cancer) and PSA response (in recurrent prostate cancer) have been published [JNCI 96:487-488, 2004; J Clin Oncol 17, 3461-3467, 1999; J Clin Oncol 26:1148-1159, 2008]. In addition, the Gynecologic Cancer Intergroup has developed CA-125 progression criteria which are to be integrated with objective tumor assessment for use in first-line trials in ovarian cancer [JNCI 92:1534-1535, 2000].

Cytology, Histology: These techniques can be used to differentiate between partial responses (PR) and complete responses (CR) in rare cases (e.g., residual lesions in tumor types, such as germ cell tumors, where known residual benign tumors can remain).

The cytological confirmation of the neoplastic origin of any effusion that appears or worsens during treatment when the measurable tumor has met criteria for response or stable disease is mandatory to differentiate between response or stable disease (an effusion may be a side effect of the treatment) and progressive disease.

FDG-PET: While FDG-PET response assessments need additional study, it is sometimes reasonable to incorporate the use of FDG-PET scanning to complement CT scanning in assessment of progression (particularly possible 'new' disease). New lesions on the basis of FDG-PET imaging can be identified according to the following algorithm:

- Negative FDG-PET at baseline, with a positive FDG-PET at follow-up is a sign of PD based on a new lesion.
- No FDG-PET at baseline and a positive FDG-PET at follow-up: If the positive FDG-PET at follow-up corresponds to a new site of disease confirmed by CT, this is PD. If the positive FDG-PET at follow-up is not confirmed as a new site of disease on CT, additional follow-up CT scans are needed to determine if there is truly progression occurring at that site (if so, the date of PD will be the date of the initial abnormal FDG-PET scan). If the positive FDG-PET at follow-up corresponds to a pre-existing site of disease on CT that is not progressing on the basis of the anatomic images, this is not PD.
- FDG-PET may be used to upgrade a response to a CR in a manner similar to a biopsy in cases where a residual radiographic abnormality is thought to represent fibrosis or scarring. The use of FDG-PET in this circumstance should be prospectively described in the protocol and supported by disease-specific medical literature for the indication. However, it must be acknowledged that both approaches may lead to false positive CR due to limitations of FDG-PET and biopsy resolution/sensitivity.

Note: A 'positive' FDG-PET scan lesion means one which is FDG avid with an uptake greater than twice that of the surrounding tissue on the attenuation corrected image.

12.4 Response Criteria

12.4.1 Evaluation of Target Lesions

Complete Response (CR): Disappearance of all target lesions. Any pathological lymph nodes (whether target or non-target) must have reduction in short axis to <10 mm.

Partial Response (PR): At least a 30% decrease in the sum of the diameters of target lesions, taking as reference the baseline sum diameters.

Progressive Disease (PD): At least a 20% increase in the sum of the diameters of target lesions, taking as reference the smallest sum on study (this includes the baseline sum if that is the smallest on study). In addition to the relative increase of 20%, the sum must also demonstrate an absolute increase of at least 5 mm. (Note: the appearance of one or more new lesions is also considered progressions).

Stable Disease (SD): Neither sufficient shrinkage to qualify for PR nor sufficient increase to qualify for PD, taking as reference the smallest sum diameters while on study.

12.4.2 Evaluation of Non-Target Lesions

Complete Response (CR): Disappearance of all non-target lesions and

normalization of tumor marker level. All lymph nodes must be non-pathological in size (<10 mm short axis).

Note: If tumor markers are initially above the upper normal limit, they must normalize for a patient to be considered in complete clinical response.

Non-CR/Non-PD: Persistence of one or more non-target lesion(s) and/or maintenance of tumor marker level above the normal limits.

Progressive Disease (PD): Appearance of one or more new lesions and/or unequivocal progression of existing non-target lesions. Unequivocal progression should not normally trump target lesion status. It must be representative of overall disease status change, not a single lesion increase.

Although a clear progression of “non-target” lesions only is exceptional, the opinion of the treating physician should prevail in such circumstances, and the progression status should be confirmed at a later time by the review panel (or Principal Investigator).

12.4.3 Evaluation of Best Overall Response

The best overall response is the best response recorded from the start of the treatment until disease progression/recurrence (taking as reference for progressive disease the smallest measurements recorded since the treatment started). The patient's best response assignment will depend on the achievement of both measurement and confirmation criteria.

For Patients with Measurable Disease (i.e., Target Disease)

Target Lesions	Non-Target Lesions	New Lesions	Overall Response	Best Overall Response when Confirmation is Required*
CR	CR	No	CR	>4 wks. Confirmation**
CR	Non-CR/Non-PD	No	PR	>4 wks. Confirmation**
CR	Not evaluated	No	PR	
PR	Non-CR/Non-PD/not evaluated	No	PR	
SD	Non-CR/Non-PD/not evaluated	No	SD	Documented at least once >4 wks. from baseline**
PD	Any	Yes or No	PD	no prior SD, PR or CR
Any	PD***	Yes or No	PD	
Any	Any	Yes	PD	

* See RECIST 1.1 manuscript for further details on what is evidence of a new lesion.
 ** Only for non-randomized trials with response as primary endpoint.
 *** In exceptional circumstances, unequivocal progression in non-target lesions may be accepted as disease progression.
 Note: Patients with a global deterioration of health status requiring discontinuation of treatment without objective evidence of disease progression at that time should be reported as “symptomatic deterioration.” Every effort should be made to document the objective progression even after discontinuation of treatment.

For Patients with Non-Measurable Disease (i.e., Non-Target Disease)

Non-Target Lesions	New Lesions	Overall Response
CR	No	CR
Non-CR/non-PD	No	Non-CR/non-PD*
Not all evaluated	No	not evaluated
Unequivocal PD	Yes or No	PD
Any	Yes	PD
* ‘Non-CR/non-PD’ is preferred over ‘stable disease’ for non-target disease since SD is increasingly used as an endpoint for assessment of efficacy in some trials so to assign this category when no lesions can be measured is not advised		

12.4.4 Duration of Response

Duration of overall response: The duration of overall response is measured from the time measurement criteria are met for CR or PR (whichever is first recorded) until the first date that recurrent or progressive disease is objectively documented (taking as reference for progressive disease the smallest measurements recorded since the treatment started).

The duration of overall CR is measured from the time measurement criteria are first met for CR until the first date that progressive disease is objectively documented.

Duration of stable disease: Stable disease is measured from the start of the treatment until the criteria for progression are met, taking as reference the smallest measurements recorded since the treatment started, including the baseline measurements.

12.4.5 Progression-Free Survival

Progression-free survival is defined as the duration of time from start of treatment to time of progression or death, whichever occurs first.

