5.4 Duration of Therapy

If at any time the constraints of this protocol are considered to be detrimental to the patient's health and/or the patient no longer wishes to continue protocol therapy, the protocol therapy should be discontinued and the reason(s) for discontinuation documented in the case report forms.

In the absence of treatment delays due to adverse events, treatment may continue indefinitely until one of the following criteria applies:

- Documented and confirmed disease progression
- Death
- Adverse event(s) that, in the judgment of the investigator, may cause severe or permanent harm or which rule out continuation of study drug
- General or specific changes in the patient's condition render the patient unacceptable for further treatment in the judgment of the investigator
- Suspected pregnancy
- Serious non-compliance with the study protocol
- Lost to follow-up
- Patient withdraws consent
- Investigator removes the patient from study
- The Siteman Cancer Center decides to close the study

Patients who prematurely discontinue treatment for any reason other than withdrawal of consent will be followed as indicated in the study calendar.

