5.5 Duration of Follow-up

After cessation of study treatment, patients will be followed every 3 months until death. Either phone contact or review of the Social Security Death Index is acceptable to monitor for overall survival. Patients removed from study for unacceptable adverse events will be followed until resolution or stabilization of the adverse event.

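### PFS runs to any later death, but scheduled tumour assessment ends with treatment and no censoring rule is given, so unseen progression after stopping biases PFS upward

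*Combined protocol and SAP*

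**What the plan says.** - **Definition.** Section 12.4.5: "Progression-free survival is defined as the duration of time from start of treatment to time of progression or death, whichever occurs first". It sets no limit on the gap between the last scan and death. Section 15.2 analyses PFS by Kaplan-Meier, overall and by biomarker group, and uses Cox models for the biomarkers. It states no censoring rule either.
- **Tumour assessment.** In the section 10.0 calendar, CT is marked at screening, under "End of every even-numbered cycle", and at end of treatment. The follow-up column is empty. Section 11.0 schedules the Tumor Measurement Form at "Baseline, end of every even numbered cycle, and end of treatment".
- **Stopping early.** Section 5.4 lists reasons other than progression, among them "Adverse event(s) that, in the judgment of the investigator, may cause severe or permanent harm or which rule out continuation of study drug". It then says: "Patients who prematurely discontinue treatment for any reason other than withdrawal of consent will be followed as indicated in the study calendar".
- **Follow-up.** Section 5.5: "After cessation of study treatment, patients will be followed every 3 months until death". It adds: "Either phone contact or review of the Social Security Death Index is acceptable to monitor for overall survival". Section 11.0 lists a Follow Up Form every 3 months; its fields are not shown.
- **Wording that points the other way.** Section 12.1 asks for re-evaluation at 8 weeks and at 8-week intervals after that, with no stated end. The note on symptomatic deterioration in section 12.4.3 says: "Every effort should be made to document the objective progression even after discontinuation of treatment". Neither is carried into the calendar or the form schedule.

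**The concern.** Once a patient stops treatment without progression, the schedules provide for no further tumour assessment, but the date of death will still be found. Under 12.4.5 that death is the PFS event, however long after the last scan it falls. If the patient progressed in between and nobody recorded it, PFS equals overall survival for that patient. A missed progression can only lengthen the recorded time, so the Kaplan-Meier estimate is pushed upward.

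This is more than an unstated detail, because the definition applied literally to the scheduled data gives the biased figure. PFS is the first secondary objective (section 2.2). It is also an outcome in the sVEGFR2 and PlGF analyses, where survival-length times would be mixed in with progression times. For patients who stopped early and are still alive at the analysis, the plan gives no rule at all, so the result would rest on an unrecorded choice.

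**Working it through.** **The plan's own figures.** The documents give no sample size, event count or power for PFS, so there is no PFS figure to reproduce. The only design calculation is for the primary endpoint. The rule of 17 or more of 56 has an exact one-sided significance level of 4.32%, as section 15.1 states. Its exact power at 35% is 80.64%, where 81.64% is printed; that is a separate matter. Neither figure uses PFS.

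**Inputs.**
- Median PFS of 4.6 months (section 1.2). It comes from previously treated patients and is taken here as an assumption.
- 8-weekly scans (section 12.1).
- Assumed: exponential times; median survival of 8 months after progression; stopping at a time uniform between 0.5 and 3 months in 15% or 30% of patients, if they have not progressed first; no progression captured after stopping.

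**Step 1: 6-month PFS with scans continued.** The progression rate is λ = ln 2 / 4.6 = 0.1507 per month. The last scan before 6 months is at week 24, or 5.52 months. PFS at 6 months is about exp(−0.1507 × 5.52) = 43.5%.

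**Step 2: share who stop without progression.** The mean of exp(−λu) for u from 0.5 to 3 is (0.9274 − 0.6363) / (0.1507 × 2.5) = 0.773. So 15% assigned gives 0.15 × 0.773 = 11.6% stopping, and 30% gives 23.2%.

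**Step 3: excess per stopper at 6 months.**
- Progression-free if scans continued: 0.435 / 0.773 = 0.563.
- Alive, and so counted progression-free under 12.4.5: for a stop at u, with d = 6 − u and μ = ln 2 / 8 = 0.0866, this is exp(−λd) + λ/(λ − μ) × [exp(−μd) − exp(−λd)]. Averaged over stoppers it is 0.911.
- Difference: 0.911 − 0.563 = 0.348.

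**Step 4: excess in the whole cohort.** 0.116 × 0.348 = 4.0 points; 0.232 × 0.348 = 8.1 points. If half of these progressions were captured on time after treatment, the excess would halve, to about 2 and 4 points.

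**Simulation under the same assumptions, including the proposed rule** (6-month PFS):

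| Scenario | Scans continued | As written | 16-week rule |
|---|---|---|---|
| 12% stop | 43.5% | 47.6% | 42.3% |
| 23% stop | 43.4% | 51.4% | 40.5% |
| 30% assigned, stoppers at twice the hazard (18% stop) | 36.1% | 43.8% | 36.8% |

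The first two rows agree with steps 1 to 4 to within 0.2 points. In the third row the hazards of progression and of death after progression are both doubled. At 12 months the as-written figure is about 24% against 19% (12% stopping) and 29% against 19% (23% stopping).

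**Median.** At 12% stopping the scan-read median is 5.5 months either way. At 23% in this model it passes 6 months, since 51.4% are still counted progression-free then.

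**A second stopping model.** Here stopping is spread over the whole time to progression, and survival after progression is calibrated to the 12.5-month median survival in section 1.2. With exact progression times, 10% to 40% stopping moves 6-month PFS from about 40% to between 42% and 50%, and the median from 4.6 to between 4.8 and 6.1 months. The scan-read median stays at 5.5 months up to 30% stopping and reaches 7.1 months at 40%.

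**Against sampling error.** With 56 patients the standard error at 43.5% is √(0.435 × 0.565 / 56) = 6.6 points, so a 95% interval extends about 1.96 × 6.6 = 13 points each way.

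**The case against.** **A reader might infer that the plan rules out tumour assessment after treatment.** It does not. Section 12.1 sets no end to the 8-weekly re-evaluation, and section 12.4.3 asks for effort to document progression after stopping. What stands is that 12.1 is not reconciled with the calendar and form schedule, and that the 12.4.3 request sits in a note on one situation, with no schedule. The figures assume no capture after treatment, which is the worst case.

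**A reader might infer that follow-up collects vital status only.** The sentence on phone contact and the death index concerns overall survival, and the calendar's follow-up column is blank even for the survival contacts that section 5.5 requires. The Follow Up Form may already ask about progression. The documents do not show it either way.

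**The stopping rate is not in the documents.** Section 1.3 describes an older, frail population but also calls the drug well tolerated, and section 6.0 offers many dose reductions short of stopping. The documents do not establish that stopping without progression will be common.

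**The bias is smaller than sampling error.** That is correct in the main scenarios. It is systematic, however, and the reported interval makes no allowance for it.

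**Progression or death, whichever is first, is a conventional definition, and censoring brings its own bias.** Both points are fair. The 16-week rule reads low when stopping is unrelated to prognosis, because early deaths count as events while survivors are censored. It reads slightly high when stoppers do worse. In the three scenarios tabulated it is closer to the truth than the definition as written.

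**Conclusion.** The point holds as a correction to a descriptive secondary endpoint. The written definition, applied to the scheduled data, credits unseen progressors with PFS until death. Under the stated assumptions this adds about 4 points to 6-month PFS at 12% stopping and about 8 at 23%, with little or no change in the scan-read median at 12%. The size rests on the assumed stopping rate, on no progression being captured after treatment, and on a median PFS borrowed from previously treated patients. Capture under sections 12.1 or 12.4.3 would shrink it in proportion.

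It would go too far to say that the bias always favours the drug. The trial has one arm, PFS has no benchmark, test or decision rule, and no direction has been shown for the biomarker hazard ratios. If the analyst chose to censor at the last scan, the problem would be possibly informative censoring instead of inflation. The clinical benefit test, the sample size of 56 and the cut-off of 17 do not use the PFS definition and are untouched.

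**What to change.** - **Sections 12.4.5 and 15.2.** Count as PFS events RECIST progression, or death within 16 weeks (two scan intervals) of the last adequate tumour assessment. Otherwise censor at the last adequate assessment, including for patients alive at the analysis. Define an adequate assessment. Report the present definition alongside as a sensitivity analysis.
- **Follow Up Form.** Make sure the existing 3-monthly form captures any known progression date and the start of new anticancer therapy for patients who stopped without progression.
- **Reconciliation.** Bring sections 12.1 and 12.4.3 into line with sections 10.0 and 11.0, so that it is clear whether tumour assessment is expected after treatment ends. The sponsor decides which is meant.

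The cost is a few sentences and at most two form fields; the analysis rule needs no additional scans. The downside is that censoring may be informative. At 6 months the rule reads 1 to 3 points low under the main assumptions (43.5 − 42.3 = 1.2; 43.4 − 40.5 = 2.9) and about 1 point high if stoppers have twice the hazard (36.8 − 36.1 = 0.7), which is why both versions should be shown. The rule can be fixed at any time before analysis, but progression dates become harder to recover as time passes.
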